Study Protocol

TITLE: **Long Term Follow-up of Deep Brain Stimulation for Treatment-Resistant Depression (LTF of DBS for TRD)**

PRINCIPAL INVESTIGATOR: **[name] (Psychiatry and Surgery)**

CO-INVESTIGATORS: **[name] (Neurosurgery)**
[name]

DRAFT DATE: **August 4, 2022**

Schema

Recruitment: Patients enrolled in DBS for TRD will be informed of the option to enroll in the naturalistic follow-up study. Patients will be informed of the option during the screening phase of the DBS for TRD study as well as a reminder 2 weeks prior to completion of the study

Study Visits: Assessment by study psychiatrist once per year

1.0 INTRODUCTION

Major Depression is one of the most common and costly of all psychiatric disorders¹. It ranks among the top causes of worldwide disease burden and is the leading source of disability in adults in North America under the age of 50². While depression can be effectively treated in the majority of patients by either medication or some form of evidence-based psychotherapy³, up to 20% of patients fail to respond to standard interventions^{4,5}. For these patients, trial-and-error combinations of multiple medications and electroconvulsive therapy are often required^{6,7}. For patients who remain severely depressed despite these aggressive approaches, new strategies are needed.

Converging clinical, biochemical, neuroimaging, and post-mortem data suggest depression is unlikely to be a disease of a single brain region or neurotransmitter system. Rather, it is now generally viewed as a systems-level disorder affecting integrated pathways linking select cortical, subcortical and limbic sites and their related neurotransmitter and molecular mediators⁸⁻¹². While mechanisms driving this ‘system dysfunction’ are not yet characterized, they are likely to be multi-factorial, with important and synergistic contributions from genetic vulnerability, developmental insults, and environmental stressors¹³⁻¹⁵. Treatments for depression can be similarly viewed within this limbic-cortical system framework, where different modes of treatment modulate specific regional targets, resulting in a variety of complementary, adaptive chemical and molecular changes that re-establish a normal mood state^{12,16,17}.

Functional neuroimaging studies have played a critical role in characterizing these limbic-cortical pathways¹⁷⁻²⁰. Previous studies have demonstrated consistent involvement of the subgenual cingulate (Cg25) in both acute sadness and antidepressant treatment effects, suggesting a critical role for this region in modulating negative mood states^{21,22}. In support of this hypothesis, a decrease in Cg25 activity is reported with clinical response to different antidepressant treatments including specific serotonin reuptake inhibitor (SSRI) antidepressant medications, electroconvulsive therapy (ECT), repetitive transcranial magnetic stimulation (rTMS), and ablative surgery²³⁻²⁸. In addition, Cg25 connections to the brainstem, hypothalamus, and insula have been implicated in the disturbances of circadian regulation associated with depression (sleep, appetite, libido, neuroendocrine changes)²⁹⁻³³. Reciprocal pathways linking Cg25 to orbitofrontal, medial prefrontal, and various parts of the anterior and posterior cingulate cortices form the neuroanatomical substrates by which primary autonomic and homeostatic processes influence various aspects of learning, memory, motivation and reward – core behaviors altered in depressed patients^{31,34-36}.

Recent advances in the surgical treatment of Parkinson’s disease have demonstrated that chronic high frequency deep brain stimulation (DBS) in pathologically active brain circuits produces profound clinical benefits³⁷⁻³⁹. It has also been shown that clinically effective DBS in the basal ganglia produces both local and remote changes in neural activity as assessed by positron emission tomography (PET)^{40,41}.

A second sham-controlled pilot study at Emory University assessed the safety and efficacy of bilateral SCC DBS in 10 TRD patients with major depressive disorder (MDD) and 7 TRD patients with bipolar II disorder (BP). [name] was the lead psychiatrist on this study. Rates of response ($\geq 50\%$ decreased in depression severity from baseline) were 41% at 6 months, 36% at 1 year and 92% at 2 years following onset of chronic stimulation. Rates of remission (virtually no depressive symptoms) were 18% at 6 months, 36% at 1 year and 58% at 2 years following onset of chronic stimulation. There was a very modest but statistically significant decrease in depression severity following 4 weeks of sham stimulation, but this was largely accounted for by a decrease in depression severity following surgery but prior to the onset of sham stimulation. In three patients in whom blinded discontinuation was performed after 24 weeks of active stimulation, all had a full return of depressive symptoms within two weeks and antidepressant benefit returned with re-initiation of stimulation. There was only one patient who experienced a serious adverse event (infection requiring removal of the system) related to surgery. There were no adverse events associated with acute or chronic stimulation. In this study, a longer duration of a euthymic (no depression) period since illness onset, fewer adequate antidepressant treatments in the current episode, fewer lifetime psychotropic medications and fewer depressive episodes each predicted response/remission at various time points in the study. It was also demonstrated that functional connectivity of the BA25/SCC region (derived from pre-operative resting state functional magnetic resonance imaging [rfMRI] data) predicted 6 month treatment response. If validated, this would support using clinical variables related to illness stability (number of episodes, time between episodes and number of treatments) as well as pre-operative rfMRI to help with patient selection if SCC DBS is introduced clinically.

In both of these prior SCC DBS studies, all patients initially received bilateral stimulation; this decision was made based on previous imaging studies implicating both left and right BA25/SCC in TRD; however, both sides were rarely implicated in the same study. In the Toronto cohort, it was discovered that one patient had a greater antidepressant response with left-sided stimulation only. At Emory, one patient was eventually found to have a greater antidepressant response to right-sided stimulation alone compared to bilateral stimulation. A single case report from an Argentinean group also described antidepressant benefit from right-sided stimulation alone¹⁸. Further evidence supports differential roles for left- and right-sided brain regions in the pathophysiology of depression¹⁹ but also suggests the nature of this laterality may differ across depressed patients. These data suggest that certain TRD patients may require right-sided stimulation, others may require left-sided stimulation and some may require stimulation bilaterally. If unilateral stimulation is comparable to bilateral stimulation, then this would allow the overall procedure to be safer since the major risk of implantation comes from the potential for an intracranial hemorrhage with each passage of a DBS lead. Additionally, this would speak to both the mechanism of action of DBS and potential neurobiological differences between TRD patients.

This pilot study supports the hypothesis that high-frequency DBS in Cg25 white matter can be used to treat depression, but further data is needed to confirm these findings. The long-term effects of DBS are not known. The following study will evaluate right versus left-sided DBS in Cg25 over the course of ten years. Patients who are enrolled in the DBS for TRD study at DHMC will be given the opportunity to enroll in the ten year follow-up study at the end of the study in which they are currently enrolled.

2.0 OBJECTIVES

We propose to test whether long-term high frequency DBS of the subgenual cingulate white matter (Cg25-DBS) is a safe and efficacious antidepressant treatment in five (5) TRD patients. We will address the following specific aims.

Specific Aim 1. To assess the long term effects including efficacy and safety of Cg25 DBS in patients with Major Depressive Disorder.

3.0 PATIENT SELECTION

Patients who are enrolled in the DBS for TRD study at DHMC will be given the opportunity to enroll in the ten year follow-up study at the end of the DBS for TRD study in which they are currently enrolled. Patients will be informed of the option during the screening phase of the DBS for TRD study as well as a reminder 2 weeks prior to completion of the study. A total of five (5) patients will be enrolled in this study.

3.1 Eligibility Criteria

- 3.1.1 Have received DBS for TRD
- 3.1.2 Ability to provide written informed consent
- 3.1.3 Willing to comply with all necessary study visits

4.0 CLINICAL ASSESSMENTS

During this phase, patients will be evaluated every 12 months by the study psychiatrist (via in-person, phone or video call visit) to assess device functioning, adverse events and current status of depression. This visit will be documented in a note to file. Specific areas to be assessed:

1. Current status of depression and overall functioning
2. Changes in medications
3. Adverse events
4. Status of DBS system including any changes or problems
5. If a patient chooses to have the DBS system explanted or turned off, they will be monitored weekly (by telephone, video call or in person as appropriate) for 12 weeks following explantation for adverse events. After that time, their participation in the study will be concluded.

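### Efficacy is part of the only aim, but no standardised depression severity score and no reference score is required at any annual contact

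*Combined protocol and SAP*

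**What the plan says.** Section 2.0 (Objectives) proposes to test whether long-term stimulation "is a safe and efficacious antidepressant treatment in five (5) TRD patients". Its single specific aim is "To assess the long term effects including efficacy and safety of Cg25 DBS" in major depressive disorder. The end of section 1.0 (Introduction) adds a second purpose, the evaluation of right- against left-sided stimulation over ten years.

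Section 4.0 (Clinical Assessments) is the only text on outcome collection. The visit takes place every 12 months, "via in-person, phone or video call visit". The depression item is "Current status of depression and overall functioning". The other areas are "Changes in medications", adverse events, and the state of the DBS system. On recording it says: "This visit will be documented in a note to file".

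The Schema describes the same light design. Patients may choose "to enroll in the naturalistic follow-up study", and the visit schedule is "Assessment by study psychiatrist once per year". Section 5.0 declares the data descriptive and plans no formal analysis. Section 3.0 sets enrolment at five patients, all of whom have already received DBS (section 3.1).

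**The concern.** Efficacy means change in depression relative to something. The protocol's own background uses the word that way: for the earlier sham-controlled pilot, section 1.0 defines response as a fall in severity of at least 50% from baseline. The follow-up study requires neither a severity score nor a baseline.

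Two psychiatrists, or one psychiatrist in two different years, could both follow section 4.0 exactly and leave notes that cannot be put on a common scale. The contact mode may also change from year to year, and recording it is not required. At stake is the efficacy half of the only aim, together with the right-versus-left purpose. A severity score not taken at a visit cannot be reliably recovered later from a narrative note. Safety collection is not affected.

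**Working it through.** The plan contains no design calculation to reproduce: five patients are stated without power, alpha or effect size. The check is therefore mainly a comparison of the sections, with some arithmetic to size the gap and the gain.

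**1. Purpose against data.**

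| A descriptive account of efficacy needs | What the protocol requires |
|---|---|
| The same severity measure each year | Current status, with no scale named in any section (4.0) |
| A reference score | None named, whether pre-implant, end of the parent DBS for TRD study, or entry to follow-up |
| Known measurement conditions | Three contact modes allowed; recording of mode not required (4.0) |
| A planned presentation | Descriptive only; no listing specified (5.0) |
| For right versus left: the above, by side | No severity measure to set against side (1.0, 4.0) |

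**2. Number of contacts affected.** Inputs are 5 patients (section 3.0), 10 years (sections 1.0 and 3.0) and one contact a year (section 4.0).

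5 x 10 x 1 = 50 contacts at most. This is a ceiling, because under section 4.0, item 5, participation ends after 12 weeks of monitoring once a patient has the system explanted or turned off.

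**3. What a scale could deliver with n = 5.** Take 3 responders of 5 as an example. The exact (Clopper-Pearson) 95% limits are:

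- lower: 2.5% quantile of Beta(3, 3) = 14.7%
- upper: 97.5% quantile of Beta(4, 2) = 94.7%

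Even 5 of 5 gives 47.8% to 100%. A response rate would say almost nothing. What a scale can yield is up to five individual trajectories.

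**4. Which reference.** Every patient enters after implantation, so every score taken in this study is a post-DBS score. Only a pre-implant score from the parent study can show change against the untreated state. A first follow-up score can show only whether the state at the start of follow-up lasts. It would also be one of the ten annual scores, leaving at most 9 changes per patient, or 5 x 9 = 45 in all. Using one reference for some patients and the other for the rest would remove the comparability between patients that the score is meant to give.

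**5. Rating time.** The documents give no duration, so 15 to 45 minutes per rating is assumed.

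- Total: 50 x 0.25 h = 12.5 h to 50 x 0.75 h = 37.5 h
- Per patient over ten years: 10 x 0.25 h = 2.5 h to 10 x 0.75 h = 7.5 h

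**The case against.** The strongest reply is that light follow-up is a declared choice. The study is naturalistic, has five patients and is descriptive only. That stands as an answer to any demand for a hypothesis test, a power calculation or a response rate, and none is asked for here. It does not answer the point itself, because a description of efficacy still needs a consistent measure and something to compare it with.

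A second reply is that the psychiatrist may use a scale anyway, and that the parent study may hold scores. Both are possible. A reader might infer that no severity data will exist, or that the notes cannot be compared. The documents do not support that: a note to file can contain a score, and the parent protocol is not among them. What they do support is that a score is not required and that no parent-study score is referred to.

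A reader might also infer that depressive episodes between visits will go unrecorded. That is not supported either. Section 4.0 lists areas to be assessed, not interview questions, so the absence of an explicit question about the past year is weak evidence that none is asked. Medication changes, adverse events, DBS system changes, hospitalisation as a serious adverse event (6.5) and reasons for withdrawal reported to the DSMB (6.3) can each reveal a relapse.

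Finally, the gain is modest. With five patients it is limited to individual trajectories, and its value against the pre-implant state depends on what the parent study holds.

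**Conclusion.** The point holds in limited form. The stated purposes include long-term efficacy and a right-versus-left evaluation, yet no standardised severity measure and no reference score is required at any of up to 50 annual contacts. Followed as written, the plan does not ensure that severity can be compared over time or between patients, even descriptively.

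This should be corrected, by adding the measure or by narrowing the purpose. It is not a safety defect and does not call for formal inference. Confidence is high that the requirement is absent from the text. It is lower on the size of the gain, since the content of the parent study cannot be known from these documents. The count of 50 assumes that all five patients complete ten annual contacts.

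**What to change.** In section 4.0, require the study psychiatrist to score one clinician-rated depression scale at each annual contact. It should be usable in person, by phone and by video, and preferably be the parent study's scale if it has one. Record the score and the visit mode in the note.

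Name one reference for all patients:

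- the parent study's pre-implant score, if available for all of them;
- otherwise the first follow-up score for all of them, with the result described as durability of the state at entry to follow-up and not as efficacy against the pre-implant state.

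Do not mix the two. In section 5.0, state that scores and change from the reference will be listed per patient with stimulation side, without a rate or a test.

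**Cost.** No visit is added under either reference. Rating takes about 12.5 to 37.5 hours over ten years on the assumed durations. Amending the protocol and its review by CPHS and the DSMB come on top; at an assumed 5 to 20 hours for this one-off work, the total is 12.5 + 5 = 17.5 to 37.5 + 20 = 57.5 hours. Ratings remain open-label, and scores may vary with contact mode.

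**Alternative.** If the present light follow-up is preferred, remove efficacy from the objective and Specific Aim 1 in section 2.0, and remove the right-versus-left evaluation from section 1.0. Changing section 2.0 alone would leave the latter without a measure. This route costs only the amendment and its review.

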5.0 DATA ANALYSIS AND STATISTICAL CONSIDERATIONS

Data collected in this phase are purely descriptive and no formal analysis is planned.

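### Section 4.0, item 5 ends participation after a reversible switch-off exactly as after explantation, with no exception for a patient whose stimulation is back on

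*Combined protocol and SAP*

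**What the plan says.** Section 4.0 sets the routine schedule: "patients will be evaluated every 12 months by the study psychiatrist". Each visit covers depression and functioning, medication changes, adverse events and, as item 4, "Status of DBS system including any changes or problems".

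Item 5 is the exit rule. Its trigger is "If a patient chooses to have the DBS system explanted or turned off". The patient is then contacted weekly "for 12 weeks following explantation for adverse events. After that time, their participation in the study will be concluded".

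Other sections bear on it as follows:

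- Section 2.0 has one specific aim, the long-term efficacy and safety of Cg25 DBS.
- Section 3.0 fixes the sample at five and gives one entry point: patients "will be given the opportunity to enroll in the ten year follow-up study at the end of the DBS for TRD study". Criterion 3.1.1 asks only that they "Have received DBS for TRD".
- Section 1.0 says that follow-up runs for ten years. It also describes three patients in a prior pilot whose stimulation was stopped under blinding: "all had a full return of depressive symptoms within two weeks and antidepressant benefit returned with re-initiation of stimulation".
- Section 5.0 states: "Data collected in this phase are purely descriptive and no formal analysis is planned".

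**The concern.** Two different events share one trigger and one consequence. Explantation ends the studied treatment for good. Switch-off leaves the hardware in place and can be undone, as the pilot described in Section 1.0 shows. Item 5 treats them alike: after 12 weeks the patient is out, whether or not stimulation has been restarted.

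A patient who stops, regrets it and is back on stimulation within the window is again receiving exactly what Aim 1 studies. Under the rule as written that patient's later yearly data would not be collected. In a five-patient descriptive study the individual courses are the whole result, so a truncated course is not averaged away.

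There is also a smaller wording gap. The trigger names switch-off, but the 12 weeks are counted only from explantation.

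**Working it through.** The plan gives no figure for this point, so there is none to reproduce. The check is of the text, followed by a simple visit count.

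**Step 1: the text**

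| Element of item 5 | Explantation | Switch-off, system left in place |
|---|---|---|
| Triggers the rule | yes | yes |
| Start of the 12 weeks stated | yes | no |
| Participation ends afterwards | yes | yes, once the 12 weeks have run |
| Exception if stimulation is on again | not applicable | none |

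No other section supplies the missing entries. Item 4 records device changes but does not exempt a pause. Section 3.0 has one entry point, the end of the parent study, so no route back is stated, even though a patient back on stimulation would still meet criterion 3.1.1. Section 6.0 deals with board review and event reporting, not with switch-off.

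**Step 2: two readings for switch-off**

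- *Natural*: the 12 weeks run from switch-off. The exit date is then defined, and a patient who has restarted by week 12 leaves anyway.
- *Strictly literal*: without explantation the clock never starts. The exit date is undefined, yearly visits may simply go on, and no yearly data are lost.

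These exclude each other. The natural reading is the better one, because on the literal reading the mention of switch-off in the trigger does no work.

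**Step 3: size on the natural reading**

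Inputs: 5 patients (Section 3.0), one visit every 12 months (Section 4.0), ten years (Section 1.0). Assumed: visits fall at years 1 to 10; one patient switches off soon after visit k, so that the 12 weeks end before the next visit; the patient restarts within the window, stays on stimulation and would have attended every visit.

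Planned visits = 5 × 10 = 50.

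Visits lost = 10 − k; share lost = (10 − k) / 50.

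| Switch-off | Visits lost | Share of 50 |
|---|---|---|
| before visit 1, window also ending before it (k = 0) | 10 | 20% |
| after visit 1 | 9 | 18% |
| after visit 5 | 5 | 10% |
| after visit 9 | 1 | 2% |

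If nobody elects switch-off, if nobody restarts, or if the literal reading is applied, the loss is 0 of 50. The documents do not say how many patients would be affected; it could be any number from 0 to 5.

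**Step 4: after the change proposed below**

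A patient who is back on stimulation at week 12 keeps the remaining 10 − k visits, so the loss in Step 3 becomes 0.

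**The case against.** The strongest case against is that this is a drafting slip with no consequence. Item 5 concerns a patient who chooses to stop, which it pairs with explantation; ending follow-up of someone who has elected to leave treatment is defensible in a naturalistic study. Interruptions for battery or programming reasons are not the patient's choice and fall under item 4. The pilot discontinuations were blinded, not elected, so they say nothing about how often a patient who asks for switch-off later restarts. Nothing formal is estimated or tested.

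Much of this stands. It limits the weight of the point but does not remove it: the rule still discharges a patient who is on the studied treatment, and nothing in the documents gives a reason for that.

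Three stronger readings are tempting and are not supported:

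- *That the plan both leaves the exit date undefined and loses data.* Only one of the two can apply to a given switch-off. The missing date taken alone is a slip that the natural reading fills.
- *That patients who switch off are left without safety cover.* On the natural reading they have 12 weeks of weekly contact. Even on the literal one, yearly adverse-event assessment continues, and Section 6.4 provides prompt reporting and board review of serious events.
- *That the study will lose up to a fifth of its visits, or that its description will be biased in a known direction.* The percentages are illustrations for one hypothetical patient. The frequency and timing of elected restart are not given, and the direction of any effect is unknown.

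**Conclusion.** The point holds as a minor one. Item 5 applies one exit rule to a final event and a reversible one, without an exception for resumed stimulation, and dates its window from only one of them. On the natural reading, a patient who has resumed by week 12 would give no further long-term data on the treatment that Aim 1 concerns.

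The size is conditional: nothing if no patient elects switch-off and then restarts; otherwise 10 − k of 50 planned visits for one such patient. That figure rests on the assumed visit years, a window run from switch-off, lasting resumption and full attendance. Data gathered before exit are kept, and an off/on episode during the weekly contacts would itself be observed. No estimate, test or decision in the plan changes.

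**What to change.** Amend item 5 in three respects:

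1. Start the 12 weeks of weekly monitoring at switch-off or, if the system is removed, at explantation.
2. End participation only after explantation (once its 12 weeks are complete) or if stimulation is still off at week 12.
3. Return a patient who has resumed stimulation by then to the planned yearly visits up to year ten, and record the off and on dates.

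I would not add a route back for restarts after week 12. It would contradict ending participation at that point, and with no contact planned afterwards the team would have no set way of learning of a restart.

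The cost is a start date and a short exception in item 5, with matching consent wording. The visits retained are yearly contacts already in the schedule, and phone or video is allowed. Decisions on whether and when to restart remain clinical.

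One limitation remains. Patients who stay off are still not followed after week 12, so continued follow-up depends on having resumed, which could favour patients who benefit. The description should therefore report those who stay off as stopped, with the date, and not leave them out.
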